12.2 SCREENING BLOOD CULTURES

At Screening, one aerobic blood culture bottle and one anaerobic blood culture bottle from two separate sites for a total of four bottles must be collected for culture (i.e., 1 aerobic and 1 anaerobic bottle from 2 separate venipuncture sites, for a total of 4 bottles).

Either an automated or a manual system can be used for blood and pleural fluid culture methods according to the preference of the local microbiological laboratory performing the testing. Refer to the Microbiology Laboratory Manual for details.

Culture results are to include identification of pathogens to the level of genus and species. Susceptibility testing for nafithromycin will not be available to the local laboratory; MICs will be assessed at the central laboratory. Therefore, decisions related to subject care (e.g., study drug discontinuation) will be based on the evolution of the clinical signs and symptoms of CABP.

12.3 SCREENING URINARY ANTIGEN TESTS

At the Screening visit, urine will be collected to test for *Legionella pneumophila* and *Streptococcus pneumoniae* antigens. Testing will be performed at the local laboratory using kits supplied by the Sponsor and the results will be recorded on the eCRF.

12.4 SEROLOGY FOR ATYPICAL BACTERIAL TITERS

At the Screening Visit and at TOC, blood samples will be collected to conduct acute and convalescent serology, respectively, for *Legionella pneumophila*, *Mycoplasma pneumoniae* and *Chlamydomphila pneumoniae* by the central laboratory.

12.5 POST-BASELINE MICROBIOLOGICAL ASSESSMENTS

At any time after the Screening Visit, respiratory specimen and blood cultures should be obtained as clinically indicated. As CABP responds to therapy, obtaining repeated specimens for culture or examination may not be clinically appropriate and/or there may be no material for culture.

If study drug is prematurely discontinued due to insufficient effect of study drug (e.g., failure at EOT or TOC, or clinical relapse at any time), an appropriate respiratory specimen and blood should be obtained for culture on the day of discontinuation; if new antibacterial therapy is administered to treat the current CABP after premature discontinuation of study drug, it is preferred that respiratory specimens and blood be collected for culture after stopping the study drug but before new treatment is started.

Blood cultures should be repeated upon knowledge of a positive result from any previous collection until sterilization is confirmed ([Table 3-1](#)).

Repeat, post-baseline urinary antigen tests for *L. pneumophila* or *S. pneumoniae* should not be performed.

12.6 CENTRAL LABORATORY PROCEDURES

With the exception of “contaminants” defined above ([Section 12.1](#)), all cultured bacterial isolates collected at each visit will be forwarded to the designated central laboratory for each study site. Central laboratory services will perform the following procedures:

1. Re-identify all bacterial isolates to the genus and species level
2. Test all bacterial isolates for nafithromycin and moxifloxacin MICs using standardized testing methodologies
3. Test Screening and TOC blood samples for atypical acute and convalescent serology, respectively, for *Legionella pneumophila*, *Mycoplasma pneumoniae* and *Chlamydomphila pneumoniae* ([Section 12.4](#))

Any questions regarding microbiological procedures, interpretation of results, or storage of isolates should be discussed with the Sponsor or designee. Additional detail is available in the Microbiology Laboratory Manual.

13.0 EFFICACY EVALUATION

13.1 PRIMARY AND SECONDARY EFFICACY VARIABLES

Primary efficacy variable:

- Clinical response at Day 4 (ITT population)

Secondary efficacy variables:

- Clinical response at Day 4 (micro-ITT population)
- Clinical outcome at EOT and TOC (ITT and CE populations)
- Improvement in CABP symptoms and normalization of vital signs at Day 4 (ITT population)
- Clinical outcome at TOC (micro-ITT population)
- By-subject and by-pathogen microbiological response at TOC (micro-ITT and ME populations)
- Hospitalization prior to FU (ITT population)

13.2 CLINICAL OUTCOME ASSESSMENTS

13.2.1 Clinical Response at Day 4

The primary efficacy endpoint is clinical response (response, non-response, or indeterminate) at Day 4, tested in the ITT Population. Clinical response (response, non-response, or indeterminate) at Day 4 will also be tested in the micro-ITT Population as a secondary efficacy endpoint. Clinical response is determined programmatically using the Investigator's determination of CABP symptoms entered into the eCRF ([Table 13.2.1-1](#)). The Investigator is not responsible for categorizing subjects as clinical response, non-response, or indeterminate at Day 4. The severity of the subject CABP symptoms of dyspnea (shortness of breath), cough, production of purulent sputum, and pleuritic chest pain will be evaluated on a 4-point scale (absent, mild, moderate, or severe) based upon the CABP Symptom Severity Guidance in [Appendix III](#).

Table 13.2.1.-1. Clinical Outcome Assessment at Day 4.

Outcome	Definition
Clinical Response	Alive and programmatically-determined improvement of at least 1 level (e.g., severe to moderate, moderate to mild, mild to absent) in at least 2 CABP symptoms (dyspnea, cough, production of purulent sputum, and pleuritic chest pain) compared to Screening, without worsening in any other symptom. Severity of symptoms is based on a 4-point scale (absent, mild, moderate, or severe) (Appendix III).
Clinical Non-Response	Meets any of the following criteria: 
 • No programmatically-determined improvement of at least 1 level in at least 2 CABP symptoms compared to Screening

Table 13.2.1.-1. Clinical Outcome Assessment at Day 4.

Outcome	Definition
	
 Worsening in any of the 4 CABP symptoms compared to Screening Requires alternative rescue antibacterial therapy for CABP prior to Day 4 Death from any cause prior to Day 4
Indeterminate	Study data are missing for evaluation of efficacy at Day 4 for any reason, including lost to follow-up.

Abbreviations: CABP = community-acquired bacterial pneumonia.

13.2.2 Clinical Outcome at EOT or TOC

An assessment of clinical outcome (cure, failure, or indeterminate) will be made by the Investigator at EOT (conducted on the day of, or within 2 days following, Day 7) or TOC (Day 15 \pm 3 days). Clinical outcome at EOT and TOC will be analyzed as secondary endpoints in the ITT and CE populations, and at TOC in the micro-ITT population.

Clinical success and clinical failure are defined in [Table 13.2.2-1](#). Clinical failure determined at any visit prior to TOC will be carried forward to subsequent assessment visits.

Table 13.2.2-1. Clinical Outcome Assessments at EOT and TOC.

Outcome	Definition
Clinical Cure	Alive and CABP is sufficiently resolved such that further antibacterial therapy is not needed. These subjects may have some residual findings related to infection (i.e., cough) requiring non-antibiotic ancillary treatment (e.g., expectorant). Criteria for clinical failure or indeterminate (below) should not be met.
Clinical Failure	Meets any of the following criteria: 
 Requires alternative rescue antibacterial treatment for CABP prior to the assessment (EOT or TOC) related to progression or worsening of CABP symptoms, development of infectious complications of CABP (e.g., empyema, lung abscess), or development of a TEAE that required discontinuation of study therapy Death from any cause prior to the assessment (EOT or TOC)
Indeterminate	Study data are missing for evaluation of efficacy at the assessment visit (EOT or TOC) for any reason, including lost to follow-up

Abbreviations: CABP = community-acquired bacterial pneumonia; EOT = End-of-Therapy; TEAE = treatment-emergent adverse event; TOC = Test-of-Cure.

13.2.3 Improvement in CABP Symptoms and Normalization of Vital signs at Study Day 4

An assessment of improvement in CABP symptoms and normalization in vital signs at Study Day 4 will be made programmatically on Day 4. Improvement in CABP symptoms and normalization in vital signs is defined in [Table 13.2.3-1](#).

Table 13.2.3-1 Improvement in CABP Symptoms and Normalization of Vital signs at Study Day 4.

Outcome	Definition
Improvement in CABP Symptoms and Normalization of Vital signs at Study Day 4	Meets all of the following criteria: 
 • Programmatically-determined improvement of at least 1 level in at least 2 CABP symptoms (dyspnea, cough, production of purulent sputum, and pleuritic chest pain) compared to Screening, without worsening in any other symptom (Appendix III) • Normalization of all vital signs: 
 ○ Temperature (oral, rectal, or tympanic) between 35.0°C and 38.0°C ○ SBP between 90 and 140 mm Hg, or return to baseline SBP \pm 5 mm Hg ○ Heart rate less than 100 beats per minute ○ Respiratory rate less than 20 breaths per minute ○ Oxygen saturation \geq 90% by pulse oximetry at room air • Ability to maintain oral intake • Normal mental status
No Improvement in CABP Symptoms and Normalization of Vital signs at Study Day 4	Does not meet all criteria for improvement in CABP symptoms and normalization in vital signs as defined above
Indeterminate	Study data are missing for evaluation of efficacy at Day 4 for any reason, including lost to follow-up.

Abbreviations: CABP = community-acquired bacterial pneumonia; SBP = systolic blood pressure.

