	
findings related to infection (i.e., cough) requiring non-antibiotic ancillary treatment (e.g., expectorant).
 
 ○ Clinical Failure: Requires alternative rescue antibacterial treatment for CABP prior to the assessment (EOT or TOC) related to progression or worsening of CABP symptoms, development of infectious complications of CABP (e.g., empyema, lung abscess), or development of a treatment-emergent adverse event (TEAE) that required discontinuation of study therapy; or death from any cause prior to the assessment. ○ Indeterminate: Study data are missing for evaluation of efficacy at the assessment visit for any reason, including lost to follow-up. 
 ● Improvement in CABP Symptoms and Normalization in Vital Signs at Study Day 4 (ITT population): Programmatically-determined improvement of at least 1 level in at least 2 CABP symptoms (dyspnea, cough, production of purulent sputum, and pleuritic chest pain) compared to Screening, without worsening in any other symptom (Appendix III), plus normalization of vital signs (temperature, blood pressure, heart rate, respiratory rate, and oxygen saturation within predefined normal ranges [Section 13.2.3]), ability to maintain oral intake and normal mental status ● By-subject and by-pathogen Microbiological Response at TOC (micro-ITT and ME populations): 
 ○ Favorable Microbiological Response: Meet criteria for eradication or presumed eradication (defined in Section 13.3) ○ Unfavorable Microbiological Response: Meets criteria for persistence or presumed persistence (defined in Section 13.3) ○ Indeterminate: Post-baseline respiratory specimen culture or blood culture was not available and the subject’s clinical response was assessed as indeterminate ● Hospitalization Prior to FU (ITT population): Hospital readmission for any reason between Day 1 and FU Visit, if previously hospitalized and discharged, or initial hospital admission for any reason between Day 2 and FU Visit, if not previously hospitalized on Day 1 (Section 13.2.4) 
Safety Endpoints:
 
Safety evaluation is based on TEAEs, clinical laboratory evaluation, vital signs, physical examination findings and electrocardiograms (ECGs) collected during the study.

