9.4.1 Premature Discontinuation from Study Drug Administration

9.4.1.1 Discontinuations Due to Safety

Possible reasons for premature discontinuation from study drug administration due to safety include, but are not limited to, the following:

- Occurrence of an AE that, in the opinion of the Investigator, warrants the subject's permanent discontinuation from study drug administration.
- Meets Hy's law criteria, defined by at least 3-fold elevations of ALT or AST above the ULN, elevation of serum total bilirubin to > 2 times ULN without elevated serum alkaline phosphatase, and no other disease or condition can be found to explain the liver test abnormalities

- Known pregnancy or breastfeeding during the study drug administration period. Female subjects whose pregnancy test is positive post-baseline must be followed through the immediate postnatal period or until termination of the pregnancy. Study center personnel must report every pregnancy as soon as possible (within 24 h of learning of the pregnancy, as described in [Section 14.1.6](#)).

Assessments and Procedures: Subjects who are prematurely discontinued from study drug administration (i.e., before the anticipated full course of study drug required for effective treatment of the CABP) for safety reasons should continue to undergo study assessments at every study visit ([Section 11.0](#)). If a subject is discontinued from study drug on Day 3 or Day 4, an attempt should be made to collect any remaining PK blood samples scheduled for that day.

Clinical Outcome Assessment: Subjects prematurely discontinued from any study drug for safety reasons and for whom further antibacterial therapy is not required for treatment of the primary infection (i.e., the CABP has resolved completely or improved to the point where no further antibacterial therapy is necessary), may be assessed as a clinical cure at the EOT and TOC visits.

Subjects prematurely discontinued from any study drug for safety reasons and who require further antibacterial therapy for the CABP should be assessed as a clinical failure on the day of discontinuation and automatically assigned an outcome of clinical failure at the next outcome evaluation time point.

9.4.1.2 *Discontinuations Due to Insufficient Therapeutic Effect*

Possible reasons for discontinuation from study drug due to insufficient therapeutic effect include, but are not limited to, the following:

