16.2.3.2 Secondary Efficacy Analyses

The secondary analysis variables are listed in [Section 13.1](#).

For analyses of the variables above that measure clinical success on a per-subject basis (i.e., clinical cure, improvement in CABP symptoms and normalization in vital signs at Day 4, lack of readmission or new admission to the hospital), the number and percentage of subjects in each treatment group in the specified population(s) classified as clinical success, clinical failure, and indeterminate (as applicable to each secondary analysis; [Section 13.2](#)) at the specified time point(s) will be tabulated. The difference between treatment groups in clinical success and 2-sided 95% CI for the difference also will be included in the tabulation.

The per-pathogen and per-subject microbiological efficacy analyses will be conducted in the micro-ITT and ME Populations at TOC. Per-subject responses will be based on per-pathogen outcomes ([Section 13.3](#)). These responses include eradication, presumed eradication, persistence, and presumed persistence. Of these responses, eradication and presumed eradication will be regarded as a favorable outcome. Persistence and presumed persistence will be regarded as an unfavorable outcome. To have an overall favorable microbiologic response, the outcome for each baseline pathogen must be favorable. Microbiological outcomes in the ME Population, by definition, will not include subjects with indeterminate responses.

The number and percentage of subjects in each treatment group recorded as having a favorable and unfavorable microbiologic response will be tabulated. Since this is an exploratory study, no statistical comparison between treatment groups is planned. In addition, a table summarizing the number and percent of all responses for each treatment group will be displayed. Individual subject data will also be displayed as a listing.

Emergent infections (i.e., superinfection, new infection) will not be considered in the by-subject or by-pathogen microbiological response and will be provided in separate listings ([Section 13.3.1](#); [Table 13.3.1-2](#)).

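### The secondary Day 4 composite in Table 13.2.3-1 has no rescue or death criterion, so a subject given another antibacterial after a safety stop can count as a success there while meeting a Non-Response criterion of the primary endpoint

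*Combined protocol and SAP*

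**What the plan says.** **Secondary Day 4 composite.** Section 13.2.3 says: "An assessment of improvement in CABP symptoms and normalization in vital signs at Study Day 4 will be made programmatically on Day 4". Table 13.2.3-1 requires improvement in at least two CABP symptoms with none worse, all vital signs in range, oral intake maintained and normal mental status. The No Improvement row reads "Does not meet all criteria for improvement in CABP symptoms and normalization in vital signs as defined above". Indeterminate covers missing Day 4 data. The synopsis gives the same content, ending with "ability to maintain oral intake and normal mental status", and has no rescue or death term either.

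**Primary Day 4 endpoint.** Table 13.2.1-1 uses the same symptom criterion, but its Non-Response row includes "Requires alternative rescue antibacterial therapy for CABP prior to Day 4" and also death before Day 4.

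**EOT and TOC.** Table 13.2.2-1 counts as failure any rescue treatment for CABP that follows worsening, infectious complications or a TEAE that ended study therapy. It also counts death.

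**Analysis.** Section 16.2.3.2 groups the composite with the other per-subject success measures ("clinical cure, improvement in CABP symptoms and normalization in vital signs at Day 4, lack of readmission or new admission to the hospital"). It tabulates subjects "classified as clinical success, clinical failure, and indeterminate", with a between-group difference and a 95% CI.

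**Visits after stopping study drug.** Under 9.4.1.1, subjects stopped for safety "should continue to undergo study assessments at every study visit". For insufficient effect, 9.4.1.2 prescribes EOT assessments on the day of stopping and safety assessments at TOC, and encourages attendance at FU. Section 9.7 names EOT, TOC and FU.

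**The concern.** The two Day 4 endpoints share a symptom criterion, a day and a population (ITT), but the written definitions treat early rescue differently and give no reason. For a rescued subject with complete Day 4 data, the composite can record as a clinical success an improvement that followed a different antibacterial. For a rescued subject without Day 4 data, the composite gives Indeterminate where the primary lists a Non-Response criterion. A reader who sets the two Day 4 tables side by side would find subjects who succeed on the composite but fail on the primary, with nothing in the plan to explain it. What is at stake is a clear, consistent classification of a secondary endpoint that is reported with a treatment difference.

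**Working it through.** **1. The plan's own figure, for scale.** Section 16.2.1 gives a 95% CI of 66.9% to 86.7% for a 78% response rate with 75 per arm. The Clopper-Pearson limits are Beta⁻¹(0.025; x, n−x+1) and Beta⁻¹(0.975; x+1, n−x). With n = 75 and x = 0.78 × 75 = 58.5 they are 66.94% and 86.75%, so the figure reproduces. (Whole counts give 66.2% to 86.2% for x = 58 and 67.7% to 87.3% for x = 59.) This interval concerns the primary endpoint. The composite has no sizing of its own.

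**2. Three hypothetical records against the definitions.**

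| Record | Table 13.2.1-1 (primary) | Table 13.2.3-1 as written | EOT/TOC |
|---|---|---|---|
| A. Stopped on Day 2 for a TEAE, another antibacterial for CABP started on Day 2, all four composite criteria met on Day 4 | Meets the rescue criterion of Non-Response | Improvement, tabulated as clinical success | Failure |
| B. Stopped on Day 3 for insufficient effect, another antibacterial started, no Day 4 data | Meets the rescue criterion of Non-Response | Indeterminate | Failure |
| C. Died on Day 3 | Meets the death criterion of Non-Response | Indeterminate or No Improvement; the table does not say which | Failure |

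Record A is the one that adds a success. Its Day 4 data are secured by 9.4.1.1. Records B and C shift subjects between the failure and indeterminate categories without adding a success.

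**3. Do other rules reach the composite?** Sections 9.4.1.1 and 9.4.1.2 make such subjects clinical failures on the day of stopping and again at the next evaluation of outcome. Section 9.7 also assigns failure on the day of stopping, and 13.2.2 carries failure forward. However, the clinical outcome row of Table 3-1 is ticked only at EOT and TOC. Footnote c of that table calls for an EOT visit on premature withdrawal from study drug. The carry-forward sentence stands in the section on Investigator-assessed EOT and TOC outcome. Section 13.2.3 is programmatic and lists its own criteria. A programmer working from Table 13.2.3-1 would have no instruction to apply those rules.

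**4. Size.** One record of type A changes an arm's success rate by 1/75 = 1.33 points. The documents give no rate of rescue before Day 4, so the number k of such subjects per arm is an assumption:

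- k = 1: 1.3 points
- k = 2: 2.7 points
- k = 3: 4.0 points
- k = 5: 6.7 points

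For comparison, the plan's interval reaches 78 − 66.9 = 11.1 points below and 86.7 − 78 = 8.7 points above its centre. If 78% is borrowed for two arms of 75, a rough Wald half-width for a difference is 1.96 × √(2 × 0.78 × 0.22 / 75) = 13.3 points. Small values of k lie well inside that.

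**The case against.** The strongest reply is that the protocol already settles record A. Section 9.4.1.1 makes that subject a failure at the next outcome evaluation; the Day 4 tables sit under a general heading on clinical outcome assessment; Table 13.2.1-1 is itself titled as a Day 4 outcome assessment; and 16.2.3.2 labels the composite in terms of success and failure. On that reading Day 4 is the next time point. This stands as a possible reading. A reader might therefore infer too much in saying that the protocol unambiguously ignores rescue on this endpoint; the documents do not support that. They leave two readings, and the schedule and the programmatic wording favour the one under which the failure rules stop at EOT and TOC.

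A reader might also infer that an arm with more early treatment failure would gain successes, so that the difference favours the worse arm. That is not shown. After insufficient effect no Day 4 assessment is specifically prescribed, although 8.1 has subjects assessed daily to Day 5. Where Day 4 data are absent the result is Indeterminate. The clearly exposed group is narrower: safety stops who also need another antibacterial before Day 4 and still meet every criterion.

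Other points stand in part. Section 7.2 does not present the composite as a stricter version of the primary, and counting observed status regardless of rescue can be a legitimate ITT choice, but the protocol does not state that choice. The study is exploratory, and 9.4.1.2 encourages at least 48 h of study drug before stopping for insufficient effect, so early rescue may be uncommon. Sections 16.2 and 16.4 defer detail, including missing data, to an SAP whose text is not in the combined document supplied. It could add a rule, but a rescued subject with complete Day 4 data is not a missing-data case.

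**Conclusion.** The inconsistency is real and limited. Table 13.2.3-1 and the synopsis do not say how rescue or death before Day 4 is classified. Read as written, they let a subject rescued after a safety stop count as a clinical success while meeting a primary Non-Response criterion and failing at EOT and TOC. Subjects rescued for insufficient effect may instead be Indeterminate here while being non-responders under the primary's rescue criterion.

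The size is 1.3 points per misclassified subject in an arm of 75. The total cannot be estimated, because the documents give neither a rescue rate nor the share of rescued subjects who would meet the composite; a percentage range built on guessed rates would be assumption only. The effect is probably small, given the short window, the narrow group and the descriptive role of the endpoint. The conclusion rests on reading the failure-assignment rules as confined to EOT and TOC. If the sponsor intends them to reach Day 4, the table still needs to say so.

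**What to change.** In the No Improvement row of Table 13.2.3-1 and in the matching synopsis text, repeat the two criteria of Table 13.2.1-1 in that table's own wording: "Requires alternative rescue antibacterial therapy for CABP prior to Day 4", and its criterion on death from any cause before Day 4. Identical wording matters, because a variant based on treatment received before the Day 4 assessment would classify rescue on Day 4 itself differently in the two endpoints.

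State that these criteria take precedence over both the Improvement and the Indeterminate rows. The same sentence could usefully cover Table 13.2.1-1, whose Response row does not itself exclude rescue. If the sponsor prefers to count observed status regardless of rescue, that should be stated as a deliberate choice and the tabulation labelled accordingly.

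The cost is a line in the table, a line in the synopsis and a condition in the program. Concomitant antimicrobials are already documented under 10.3. The composite rate may come out slightly lower. The change affects outcome classification only and leaves clinical management untouched.
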